2. LIST OF ABBREVIATIONS

ADR	Adverse Drug Reaction
AE	Adverse Event
AESI	Adverse Event of Special interest
ALT	Alanine aminotransferase
AP	Alkaline Phosphatase
AST	Aspartate aminotrasferase
ATC	Anatomical Therapeutic Chemical
CA	Competent Authority
CDA	Confidentiality Agreement
CI	Confidence Interval
CRF	Case Report Form
CRO	Contract Research Organization
CRP	C-Reactive Protein
DMP	Data Management Plan
eCRF	Electronic Case Report Form
EDC	Electronic Data Capture
ENCePP	European Network of Centres for Pharmacoepidemiology and Pharmacovigilance
EU	European Union
FDA	Food and Drug Administration
GPP	Good Pharmacoepidemiology Practice
GPP	Generalized Pustular Psoriasis
GPPASI	Psoriasis Area and Severity Index for Generalized Pustular Psoriasis
GPPGA	Physician's Global Assessment for Generalized Pustular Psoriasis
GVP	Good Pharmacovigilance Practices
IEC	Independent Ethics Committee
IRB	Institutional Review Board
ISF	Investigator Site File
IV	Intravenous
KPAC	Korean Pharmaceutical Affairs Code
KPBMA	Korea Pharmaceutical and Bio-Pharma Manufacturers Association
KRPIA	Korean Research-based Pharma Industry Association
MAH	Marketing Authorisation Holder
MedDRA	Medical Dictionary for Regulatory Activities
MFDS	Ministry of Food and Drug Safety
NCE	New Chemical Entity
ONIS	Observational and Non-Interventional Study
PASI	Psoriasis Area and Severity Index

PASS	Post-Authorisation Safety Study
PGA	Physician's Global Assessment
PMP	Project Management Plan
PMS	Post Marketing Surveillance
PPP	Palmo-Plantar Psoriasis
PRO	Patient-Reported Outcome
PSS	Psoriasis Symptom Scale
QV	Qualification Visit
RMP	Risk Management Plan
SADR	Serious Adverse Drug Reaction
SAE	Serious Adverse Event
SAP	Statistical Analysis Plan
SFQ	Site Feasibility Questionnaire
SOP	Standard Operating Procedure
VAS	Visual Analogue Scale

3. RESPONSIBLE PARTIES

An ONIS lead who is appointed by [REDACTED] is responsible for coordinating all required activities, in order to:

- manage the study in accordance with applicable regulations and internal standard operating procedures (SOPs),
- direct the study team in the preparation, conduct, and reporting of the study,
- order the materials as needed for the study,
- ensure appropriate training and information of a Contract Research Organization (CRO) and site staff.

[REDACTED] delegate study tasks such as monitoring activities, data management, statistical analysis, etc. to a CRO and the delegated tasks are performed in accordance with the applicable SOPs of CRO or Boehringer Ingelheim as described in a project management plan (PMP).

Participating study sites are general hospitals or clinics. Contact details and the list of all investigators are kept in a stand-alone document.

4. ABSTRACT

Name of company: Boehringer Ingelheim			
Name of finished medicinal product: Spevigo®			
Name of active ingredient: Interleukin inhibitor (L04AC22) / Spesolimab			
Protocol date: 08 October 2024	Study number: 1368-0122	Version/Revision: 2.0	Version/Revision date: 21 January 2025
Title of study:	A regulatory requirement non-interventional study to monitor the safety and effectiveness of Spesolimab in Korean patients with flares with generalized pustular psoriasis		
Rationale and background:	This Post Marketing Surveillance (PMS) is a local Post Authorized Safety Study (PASS) stipulated in the local PMS regulation: A surveillance that the Marketing Authorization Holder (MAH) conducts during the re-examination period (4-6 years) in order to collect, review, confirm, or verify the information regarding the safety and effectiveness of commercially licensed new drugs requiring the re-examination. This real world data is submitted to the Ministry of Food and Drug Safety (MFDS) and the surveillance results are reflected in the approved information.		

	
A 6-year PMS for Spesolimab IV was granted for treatment of generalized pustular psoriasis (GPP) flares, and safety data from 21 patients should be collected in a real world environment.
 
Because patients with more diverse conditions are enrolled in routine settings than in clinical trials, this PMS will provide additional real-world data on Spesolimab in Korean patients with GPP.

Research question and objectives:	The primary and secondary objectives are to respectively monitor the safety and effectiveness of Spesolimab IV in Korean patients with flares with GPP in a routine medical practice.
Study design:	Single-arm, open-label, multi-centre, observational and non-interventional study based on newly collected data
Population:	
Inclusion criteria:
 
 • Patients starting Spesolimab IV for the first time in accordance with the approved label in Korea (complete enumeration for the first 2 years after product launch) • Patients with GPP flare • Age \geq 19 years at enrolment • Patients who have signed the data release consent form 
Exclusion criteria:
 
 • Patients with severe or life-threatening hypersensitivity to Spesolimab or to any of the excipients • Patients with clinically important active infections (e.g. active tuberculosis)
Variables:	
Outcomes of safety:
 
All reported adverse event (AE)s in patients who take at least one dose of Spesolimab IV
 
Outcomes of effectiveness:
 
Changes in the Generalized Pustular Psoriasis Physician Global Assessment (GPPGA) pustulation sub-score (mandatory), GPPGA score (mandatory), Psoriasis Area and Severity Index for Generalized Pustular Psoriasis (GPPASI) (if collected), pain Visual Analog Scale (VAS) (if collected) and Psoriasis Symptom Scale (PSS) (if collected) from baseline after 1 week and/or 4 weeks

Data sources:	Patients' medical records
Study size:	21 patients
Data analysis:	All statistical analyses will be explorative in nature. Patient characteristics will be reported using measures of central tendency (e.g., mean, median) and variance (standard deviation, quartiles) for continuous variables and using frequencies and percentages for count data. Frequency of safety events will be reported using frequencies and incidence with 95% confidence interval (CI). The changes of the effectiveness outcomes from baseline will be compared in an exploratory sense via paired t-test.
Milestones:	
Start of data collection: March 2025
 
End of data collection: August 2029
 
Final study report: November 2029

5. AMENDMENTS AND UPDATES

Number	Date	Section of study protocol	Amendment or update	Reason
1	20 January 2025	9.1 Study design	· Added “complete enumeration for the first 2 years after product launch”.	Specifies that this is a complete enumeration.
2	20 January 2025	9.2.2.2 Inclusion criteria	· Added “complete enumeration for the first 2 years after product launch”.	Specifies that this is a complete enumeration.
3	20 January 2025	9.5 Study size	· Added “Complete enumeration”.	Specifies that this is a complete enumeration.
4	20 January 2025	9.7.1.2 Number of cases to safety assessment	· Added clarification that cases enrolled during the complete enumeration period are included in the safety set.	Clarifies which cases are included in the safety set.

6. MILESTONES

Milestone	Planned Date
IRB/IEC approval	FEB 2025
Start of data collection	MAR 2025
End of data collection	JUN 2029
Interim report 1-1	APR 2024
Interim report 1-2	OCT 2024
Interim report 2-1	APR 2025
Interim report 2-2	OCT 2025
Interim report 3	OCT 2026
Interim report 4	OCT 2027
Interim report 5	OCT 2028
Registration in the EU PAS register	JUL 2024
Final report of study results:	NOV 2029

* The interim reporting schedule is determined from the date of market approval in accordance with Korean regulations.

7. RATIONALE AND BACKGROUND

GPP is a severe skin disease characterized by the repeated occurrence of acute flares caused by systemic inflammation affecting the skin and internal organs [[R15-1421](#), [R16-0933](#)]. Therapeutic intervention in GPP is a major challenge. To date, there are no approved therapies indicated for treatment of GPP flares, despite the morbidity and mortality associated with GPP flares. There is limited evidence on the efficacy and safety for the use of nontargeted immunomodulatory therapies (e.g. methotrexate, cyclosporine, retinoids, systemic corticosteroids) for the treatment of GPP flares. Most of these therapies used in clinical practice are associated with toxicities that make them inappropriate for continued use [[R17-3600](#), [R19-1562](#)].

Spesolimab is an anti-IL36R antibody with a high clinical activity to block IL36R signaling as demonstrated in patients with GPP, a severe skin disease driven by uncontrolled IL36 activity [[c15875404-04](#)].

In the randomised and placebo-controlled phase II trial (1368-0013), Spesolimab showed an acceptable safety profile. The overall rates of adverse events were generally comparable between treatment groups during Week 1. Non-serious infections were reported with a higher rate in the Spesolimab group than in the placebo group, with no apparent pattern regarding pathogen and affected organs. There was no increase in the incidence rates of adverse events

after longer observation time (12 weeks) or higher exposure to Spesolimab (2 to 3 doses) [[c31523813-01](#)].

This PMS is a local PASS stipulated in the local PMS regulation: A surveillance that the MAH conducts during the re-examination period (4-6 years) in order to collect, review, confirm, or verify the information regarding the safety and effectiveness of commercially licensed new drugs requiring the re-examination. This real world data is submitted to the MFDS and the surveillance results are reflected in the approved information.

A 6-year PMS for Spesolimab IV was granted for treatment of GPP flares, and safety data from 21 patients should be collected in a real world environment.

Because patients with more diverse conditions are enrolled in routine settings than in clinical trials, this PMS will provide additional real-world data on Spesolimab in Korean patients with GPP.

8. RESEARCH QUESTION AND OBJECTIVES

8.1 PRIMARY OBJECTIVE

The primary objective is to monitor the safety profile of Spesolimab IV in Korean patients with flares with GPP in routine medical practice.

8.2 SECONDARY OBJECTIVE

The secondary objective is to monitor the effectiveness of Spesolimab IV by evaluating changes in the GPPGA pustulation sub-score (mandatory), GPPGA score (mandatory), GPPASI (if collected), pain VAS (if collected) and PSS (if collected) from baseline after 1 week and/or 4 weeks.

9. RESEARCH METHODS

9.1 STUDY DESIGN

This is a single-arm, open-label, multi-centre, observational and non-interventional study based on newly collected data.

This study will be carried out by enrolling patients in a consecutive manner into the study requiring completion of case report forms (CRFs) from the patient who is initially administered the drug following the study start date to the requested number of patients without omission (complete enumeration for the first 2 years after product launch). Prior to the initiation of the study, written contract shall be concluded, and this contract shall be concluded among [REDACTED] CRO (if applicable) and with the head of the site or the investigator with his/her consent.

Patients will be managed according to the local practice guidelines. The choice of treatment will be solely at the discretion of the investigator. Spesolimab IV will be administered according to the approved label in Korea. Hence there are no additional risks to patients by participating in this PMS.

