9.4 DATA SOURCES

This study will be carried out in the manner of successive observation that the investigator will be asked to put clinical data in an electronic data capture (EDC) system from the patient who was initially administered the drug following the study start date to the requested number of patients without omission.

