9.5 STUDY SIZE

The enrolment target is 21 patients for a total of 6 years, considering the prevalence of generalized pustular psoriasis with acute flares in Korea and the market conditions. [REDACTED] is committed to collecting data from all patients who receive Spesolimab IV within a 2-year period after the product's launch (complete enumeration).

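### Enrolment starts at study start (9.1, 9.4) but complete enumeration starts at product launch (9.5), with no stated route to enrol earlier patients or collect their pre-consent adverse events; the end of data collection also has two dates

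*Protocol*

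**What the plan says.** Section 9.1 has consecutive enrolment run "from the patient who is initially administered the drug following the study start date to the requested number of patients without omission". The same sentence closes with a parenthesis naming complete enumeration for the first two years after launch. Section 9.4 gives the rule again, "from the patient who was initially administered the drug following the study start date to the requested number of patients without omission", without the parenthesis. The first inclusion criterion (9.2.2.2) carries the parenthesis.

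Section 9.5 states the commitment: the sponsor is "committed to collecting data from all patients who receive Spesolimab IV within a 2-year period" from launch. It also says "The enrolment target is 21 patients for a total of 6 years".

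Section 9.7.1.2 normally excludes from the safety set anyone dosed before the site contract or before consent. It waives both exclusions for cases enrolled during the enumeration period. Section 9.2.3.1 collects data once consent is obtained at Visit 1. Section 11.2 sets adverse event collection from the consent signing date to the end of the study.

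On dates, the abstract has "End of data collection: August 2029", while the table in Section 6 has June 2029. Both start data collection in March 2025. No launch date appears anywhere.

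**The concern.** Study start and product launch are different clocks. A site that follows 9.4 as written would not enrol a patient treated after launch but before study start, although 9.5 promises that patient's data. Complete enumeration is a safeguard against selective inclusion in a single-arm study, and the ENCePP checklist in Annex 2 points to 9.1 and 9.2 for selection bias. The report could claim full enumeration when the operating rule did not deliver it.

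The second problem concerns the primary objective, safety. A patient dosed before consent may stay in the safety set, yet events between dose and consent are outside the window in 11.2. Infusion and other systemic hypersensitivity reactions are events of special interest. A reaction to the infusion would fall in exactly that interval. Such a patient would count in the denominator while the earliest events might not count in the numerator, which biases incidence downwards.

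The two end dates are a smaller matter, but sites and the data management plan need one.

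**Working it through.** The target of 21 has no statistical derivation to reproduce. The check compares the rules and then does calendar arithmetic.

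**1. Which rule admits which patient?** Study start is taken as the planned start of data collection, March 2025.

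| Patient | 9.1 main clause and 9.4 | 9.5 | 9.7.1.2 | Adverse events under 11.2 |
|---|---|---|---|---|
| Dosed after launch, before study start | Not enrolled | Promised | Kept, but only if enrolled | From consent only |
| Dosed after study start, before contract or consent, within 2 years of launch | Enrolled | Promised | Kept | From consent only |
| Dosed after consent | Enrolled | Promised, if within 2 years of launch | Kept | Complete |

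The first row is the enrolment conflict. The first two rows share the adverse event gap.

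**2. Does 9.7.1.2 close the gap?** Section 9.1 requires the contract before the study begins. At a site contracted at the outset, a patient dosed before contract was therefore also dosed before study start, so the rule in 9.1 and 9.4 never enrols that patient and the waiver has nobody to act on. It does act where a site contracts later, or where dosing falls between study start and consent. The waiver is useful, but it governs the analysis set and not enrolment.

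**3. How large could the gap be?** Months of the 24-month enumeration window lying before study start = months from launch to March 2025, or zero if launch is later. The launch dates below are assumptions.

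- October 2023: 17 of 24 months (71%)
- April 2024: 11 of 24 (46%)
- October 2024: 5 of 24 (21%)
- March 2025 or later: 0 of 24

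Interim report 1-1 is listed for April 2024, 11 months before data collection, and the footnote in Section 6 times these reports from market approval. Approval therefore came first, but approval does not date launch. These are calendar months, not patients. The documents give no rate to convert them. One patient is 1/21 = 4.8% of the target.

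**4. Would the target of 21 close enrolment inside the enumeration period?** That needs 21 patients in 24 months, or 10.5 a year. As rough yardsticks only:

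- 21 spread evenly over 6 years is 3.5 a year, or 7 in two years.
- 21 enrolled between March 2025 and 24 weeks before 30 June 2029 (46.5 months) is 21/46.5 × 12 = 5.4 a year, or about 11 in two years.

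On neither does the cap bind. The text still conflicts, because 9.4 stops at the requested number and 9.5 does not.

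**5. End date.** June and August 2029 differ by two months. Subtracting 24 weeks (168 days), the last enrolment that allows a full Week 24 visit is 13 January 2029 for a 30 June end, or 16 March 2029 for a 31 August end.

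**The case against.** The strongest reply is that the intent is plain. The enumeration wording sits in 9.1 itself, in the inclusion criteria and in 9.5, with a matching waiver in 9.7.1.2. Consecutive enrolment is then the general rule and enumeration the exception for two years. Anyone dosed before study start will usually have been dosed before contract or consent, the group the waiver keeps. This stands as evidence of intent, and it rules out saying that the protocol as a whole admits only patients dosed after study start. It does not settle the operating rule: 9.4 lacks the wording, the waiver presupposes enrolment, and 11.2 makes no allowance for patients dosed before consent.

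It is also fair that no loss is shown. With no launch date, zero is as compatible with the text as any other figure.

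A reader might go further and infer an accrual shortfall, because the target is set against 6 years while data collection spans about 52 to 54 months. The documents do not support that. Section 7 says "A 6-year PMS for Spesolimab IV was granted for treatment of GPP flares, and safety data from 21 patients should be collected", so the 6 years reads as the granted surveillance period, and the protocol states no accrual rate. A rate obtained by dividing 21 by 6 is the reader's own, and so is any predicted enrolment or percentage loss built on it. Nor does anything say that enrolment stays open until the end of data collection, so truncated follow-up of late patients is not established.

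**Conclusion.** The point holds as an inconsistency to be corrected. Read literally, 9.1's main clause and 9.4 leave out patients whom 9.5 promises whenever launch precedes study start. Separately, 11.2 leaves the interval from dose to consent uncovered for any patient dosed before consent, including some whom 9.7.1.2 expressly keeps.

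The size of any enrolment loss cannot be computed. It depends on the unstated launch date and on how many patients were treated in the gap, and it may be zero. The adverse event gap does not depend on launch preceding study start; it needs only one patient in the safety set dosed before consent. The cap at 21 is a conflict of wording that is unlikely to bind within the enumeration period. The June and August 2029 end dates contradict each other outright, by two months.

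**What to change.** - **Sections 9.1 and 9.4:** state that, for the enumeration period, enrolment starts with the first patient treated after product launch, and that reaching 21 does not close enrolment before that period ends.
- **Section 9.5:** give the launch date and the closing date of the enumeration period.
- **Section 11.2:** for enumeration-period patients dosed before consent, collect adverse events from the first Spesolimab IV dose, taken from medical records under the signed data release consent. Align 9.2.3.1 with this.
- **Reporting:** give the number of patients treated in the enumeration period but not enrolled, with reasons. Inclusion needs a signed consent, so some treated patients may never enter, and this count lets a reader judge whether enumeration was complete.
- **Sections 4 and 6:** use one end-of-data-collection date.

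The cost is protocol wording plus chart abstraction for any patients dosed before study start or consent. Abstraction fits imperfectly with 9.1's description of newly collected data, so that description needs a qualifier. GPPGA scores at baseline and Weeks 1 and 4 may be missing for these patients. Under 9.7.1.3 those without effectiveness information leave the effectiveness set but can stay in the safety set, which serves the primary objective.

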9.2 SETTING

9.2.1 Study sites

[REDACTED] will do our best to encourage the sites that prescribe Spesolimab IV to participate in this study as much as possible. Investigators will be mainly dermatologists.

As provided in the [Standards for Re-examination of New Drugs, Etc.] of MFDS Notification, [REDACTED] should select study site according to the following requirements:

- Equipment, facility, and manpower capable of fully achieving the goal of investigation should be held.
- The investigator should have specialized knowledge of the drug subject to investigation and the indication, have completed education/training necessary for performing the investigation, or have practical experience.
- Study site and the investigator should strictly keep confidential the record of subject's personal data.
- The investigator should be fully aware of the [Standards for Re-examination of New Drugs, Etc.] and study protocol.

9.2.1.1 Managing Site and Physician/Investigator Selection, Contracting and Training
See [Annex 3](#).

9.2.2 Study population

9.2.2.1 Main diagnosis for study entry

Patients diagnosed with GPP in Korea

9.2.2.2 Inclusion criteria

- ① Patients starting Spesolimab IV for the first time in accordance with the approved label in Korea (complete enumeration for the first 2 years after product launch)
- ② Patients with GPP flare
- ③ Age \geq 19 years at enrolment
- ④ Patients who have signed the data release consent form

9.2.2.3 Exclusion criteria

- ① Patients with Severe or life-threatening hypersensitivity to Spesolimab or to any of the excipients
- ② Patients with clinically important active infections (e.g. active tuberculosis)

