9.7.1.2 Number of cases to safety assessment

These include those who signed the data release consent form to participate in this study, took Spesolimab IV once at least, and were followed up by the investigator once or more.

Based on the MFDS guideline, the cases below shall be excluded from safety analysis (defined below):

- a. Patients who did not signed (signature missing), or patients who signed on the data release consent form prior to the contract date
- b. Patients who took Spesolimab IV prior to the contract date
- c. Patients who took Spesolimab IV prior to signing the data release consent form
- d. Patients who have not taken Spesolimab IV
- e. Patients who do not meet the inclusion/exclusion criteria
- f. Follow-up failure: Patients whose safety information cannot be obtained due to lost-to-follow-up
- g. Patients who were prescribed Spesolimab IV for indications outside the local label

However, cases enrolled during the complete enumeration period within 2 years of product launch will be included in the safety set even if the patients who took Spesolimab IV prior to the contract date or prior to signing the data release consent form.

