The term Adverse Event of Special Interest (AESI) relates to any specific AE that has been identified at the project level as being of particular concern for prospective safety monitoring and safety assessment within this study, e.g. the potential for AEs based on knowledge from other compounds in the same class.

The following are considered as AESIs:

- Systemic hypersensitivity reactions including infusion reactions and anaphylactic reactions
- Severe infection
- Opportunistic and mycobacterium tuberculosis infections

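### For complete-enumeration patients who consent after their first infusion, the undated exclusion criteria can be read to remove a patient from the safety set because of an event that began after dosing

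*Protocol*

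**What the plan says.** **Eligibility.** Protocol 9.2.2.2 admits "Patients starting Spesolimab IV for the first time in accordance with the approved label in Korea". Section 9.2.2.3 has two exclusions: "Patients with Severe or life-threatening hypersensitivity to Spesolimab or to any of the excipients", and "Patients with clinically important active infections (e.g. active tuberculosis" being the example given). Neither names a time point. The age criterion does, with the words "years at enrolment". Under 9.2.3.1 and the flow chart, the criteria are reviewed once, at Visit 1 (labelled baseline, week 0), and the data for that visit are collected after consent has been obtained.

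**Safety set.** Section 9.7.1.2 lists cases to be left out of the safety analysis. Items (b) and (c) cover dosing before the site contract or before consent. Item (e) is "Patients who do not meet the inclusion/exclusion criteria". A closing paragraph, added in version 2.0, says that cases from the two-year complete-enumeration period "will be included in the safety set even if the patients who took Spesolimab IV prior to the contract date or prior to signing" the consent form.

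**Outcome.** AESI incidence is one of the primary outcomes (9.3.2.1). Section 11.1 lists three AESI groups: "Systemic hypersensitivity reactions including infusion reactions and anaphylactic reactions", severe infection, and "Opportunistic and mycobacterium tuberculosis infections".

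**Collection and population.** Section 11.2 collects adverse events from the date the consent form is signed. Section 9.7.2 bases the safety analyses on everyone who received at least one dose.

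**The concern.** An exclusion criterion should describe the patient before exposure. Here the population is first-time IV users, so severe hypersensitivity to Spesolimab itself can hardly be present before the first infusion, apart from earlier subcutaneous or trial exposure. (Allergy to an excipient can be.) If the criterion is applied on a date after the infusion, the main way to meet the Spesolimab part of it is to have reacted to the study treatment.

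For most patients this does not arise, because consent and eligibility review come before dosing. Version 2.0 keeps a group for whom the order is reversed. If a site applies the criteria to such a patient's condition on the day of consent, a primary-outcome event becomes a reason for leaving the safety set. The study exists to monitor safety and plans 21 patients, so one lost case can decide whether an AESI is reported at all.

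**Working it through.** The protocol gives no AESI rate and bases its 21 patients on prevalence and market conditions, so there is no figure of its own to reproduce. The check is mainly a comparison of sections, followed by an illustration of size.

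**Step 1: who can be affected.** Outside the enumeration period, a patient dosed before consent is already removed by 9.7.1.2(c). Only enumeration cases that the closing paragraph keeps are left.

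**Step 2: does that group plausibly exist?** Item (a) of 9.7.1.2 removes patients who signed before the contract date, and it is not waived. A patient dosed before the contract and kept by the closing paragraph must therefore have consented after dosing. Section 6 ties the interim reports to the market approval date and puts the first in April 2024, while data collection starts in March 2025. Approval thus preceded data collection by at least about 11 months. The launch date and the number of patients treated in between are not given.

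**Step 3: does the waiver protect them?** It covers early dosing, which is items (b) and (c). It says nothing about item (e).

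**Step 4: does the baseline label supply the missing date?** For a patient who consents before dosing, yes. For a late consenter, Visit 1 is the consent visit and follows the infusion, so the label does not point to a time before dosing.

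**Step 5: how far do the exclusions overlap with the AESIs?**

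| Exclusion (9.2.2.3) | AESI (11.1) | Overlap |
|---|---|---|
| Hypersensitivity, only if severe or life-threatening | Systemic hypersensitivity including infusion reactions, no severity limit | Severe reactions only |
| Important infection, only while active | Severe, opportunistic or tuberculous infection | Only infections still active when judged |

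The overlap is partial. It covers the more serious events.

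**Step 6: size, as an illustration.** Input from 9.5: n = 21. Assumption: k affected late consenters, k = 1 to 3, no other AESI, and the event would be counted if the patient stayed in. Exact (Clopper-Pearson) 95% limits are beta quantiles: lower = Beta(0.025; k, n−k+1), upper = Beta(0.975; k+1, n−k). With no events the upper limit is 1 − 0.025^(1/n).

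| k | Kept: k/21 (95% CI) | Removed: 0/(21−k) (95% CI) |
|---|---|---|
| 1 | 4.8% (0.1–23.8) | 0/20 = 0% (0–16.8) |
| 2 | 9.5% (1.2–30.4) | 0/19 = 0% (0–17.6) |
| 3 | 14.3% (3.0–36.3) | 0/18 = 0% (0–18.5) |

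With k = 0 nothing changes.

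**Step 7: would the event be counted anyway?** Under 11.2 as written, a reaction before the consent signature falls outside the collection window. If that rule is applied strictly, keeping the patient gives 0/21, with upper limit 1 − 0.025^(1/21) = 16.1%, against 0/20 with 16.8%. The contrast in Step 6 therefore appears only if the start of collection is also moved.

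**The case against.** The strongest reply is that the criteria read naturally as conditions at the start of treatment. Inclusion ① speaks of patients starting the drug on label, and the review visit is called baseline. Section 9.2.3.1 treats what happens after initiation as adverse events, 11.2 requires AESIs to be reported within 24 hours, 9.5 commits to data from every patient treated in the enumeration period, and 9.7.2 refers to all treated patients. Removing a patient for a post-dose AESI would run against all of these.

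Much of this stands. A reader might infer that such a patient is certain to be excluded. The documents do not support that: it is one permitted reading, and several sections point the other way. What remains is that the protocol does not choose between the readings. Item (e) is a specific removal rule that the waiver leaves in force, so two sites could classify the same patient differently and both claim to follow the protocol.

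A reader might also infer that the exclusions and the AESIs are identical. They are not, as the table above shows. Nor does the argument extend to inclusion ②, on the idea that a late consenter whose flare has cleared would fail it while one still flaring would pass. Visit 1 records the date of the flare in question, and the surveillance concerns treatment of flares, so the criterion means the treated episode. Nothing requires the flare to persist at signature.

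Finally, it is fair to say that the consent-based collection window in 11.2 may by itself lose a pre-consent event. That is a second gap on the same route, and it must be closed together with the first.

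**Conclusion.** The point holds in a limited form. For enumeration-period patients who consent after their first infusion, 9.2.2.3 combined with 9.7.1.2(e) allows removal from the safety set because of a severe hypersensitivity reaction, or a still-active important infection, that began after dosing. Any resulting error has one direction: AESIs, and serious events of these kinds, can be lost but not added.

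The size is unknown. It is nil if no late consenter has such an event. One affected patient would move the observed AESI incidence from 4.8% to 0% and the upper 95% limit from 23.8% to 16.8%. This assumes that all 21 patients are otherwise evaluable, that no other AESI occurs, and that the event would be collected if the patient stayed in. The last assumption fails under a strict reading of 11.2 as it stands.

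**What to change.** Three linked changes:

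1. In 9.2.2.3 and the abstract, state that both exclusion criteria are judged on the patient's status immediately before the first Spesolimab IV infusion, from the medical record when consent comes later.
2. In 9.7.1.2, state that an event with onset at or after the start of that infusion is never grounds for exclusion under item (e).
3. In 11.2, for enumeration cases, start adverse event collection at the first dose instead of the consent signature, in line with the all-treated population in 9.7.2. Without this, the first two changes keep the patient but may not count the event.

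The eCRF eligibility page should carry the same reference time. The cost is a few sentences and a little retrospective record review for late consenters, with no added patients or procedures. The reported AESI rate may be less favourable. The changes are best made before decisions on who enters the safety set are taken with events known.
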